In the event that subjects are enrolled by the Trauma team into Part B while having an inpatient status at TUKHS, the study team, Investigational Pharmacy, and the medical team will work together to dispense, store, and administer the study medication. The study team will continue to work with the Investigational Pharmacy and medical team, as appropriate, for the duration of the subject's inpatient status while on study, as necessary to comply with this protocol.

Attrition: This is a pilot study and no previous data exists as a basis to estimate attrition for this study. Any study participant who withdraws consent or is removed from Part A or Part B of the study during the 28-day trial period or does not successfully complete the protocol required 14 days of dosing may be replaced to allow for 40 subjects who complete the protocol.

Target Duration: The target duration of the treatment intervention with OXE-103 will be two weeks. The total involvement in the study including screening and follow up assessments will be 8 weeks.

Adverse Events: Oxeia, the supplier to the study team of the OXE-103 and placebo, performs and submits safety reports to the FDA under a separate IND. As OXE-103 has already undergone safety testing and the safety profile is known, the adverse events associated with OXE-103 are included in an Investigator's Brochure written by Oxeia Biopharmaceuticals. For the purposes of this study, the study team will collect all adverse events reported by subjects including SAEs and TEAEs regardless of suspected causality, and in accordance with appropriate rules and regulations. Study team will report any that are deemed by Investigator to be:

- Unexpected AND related
- Expected but occurring at an increased frequency or severity
- Occurring in such a way that changes the risks/benefit ratio to study participants and warrants an update in consent form and/or protocol.
- All SAE's will be reported per applicable rules and regulations (IRB/FDA)

Depression Screening: The study team will administer the PHQ-9 questionnaire at specified timepoints to help identify any potential risk or need for intervention.

Safety Monitoring: Subjects participating in Part A Arm 2 (non-treatment control) will not require safety monitoring. All other subjects participating in Part A Arm 1 and Part B Arms 1 & 2 will require safety monitoring.

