Outcomes for the investigation of the effect of OXE-103 will be based on self-reported symptom scoring, quality of life questionnaires, computerized cognitive testing assessing executive function, memory and processing speed, and accelerometer-based balance scoring. Safety assessments will include collection of adverse events, clinical laboratory samples, electrocardiograms (ECGs), vital signs including body weights, suicide screening and physical/neurological examination findings.

3. Study Objectives

The primary objective of this study is to describe the change in symptom burden of subacute or acute concussion for the two treatment groups in each part, as measured by the change from baseline to Day 15 in the Post-Concussion Symptom Score questionnaire (PCSS) total score, total number of symptoms and total score for the 4 most bothersome symptoms (4MBS, as identified on Day 1). Improvements of $\geq 20\%$ will be considered clinically meaningful.

The secondary objectives are to:

- Describe the change in quality of life for the two groups in each part as measured by the change from baseline to Day 15 in the Quality of Life after Brain Injury (QOLIBRI) total score and Patient Global Assessment of Status Visual Analog Scale (PGAS VAS).
- Describe changes in cognitive performance for the two groups in each part as measured by the change from baseline to Day 15 in the BrainCheck composite score.

Exploratory objectives of the study are to:

- Describe the correlation between the change in symptom burden and quality of life during the treatment period for each group in each part.
- Describe changes in symptom burden and quality of life at different time points for the two groups in each part.

4. Sample Size

The exploratory nature of this study is such that it is not powered to yield statistically significant outcomes, but will allow detection of trends within subjects and between groups within each part, will support comparison with standard tests of neurocognitive functions, and will provide sample size estimates for future studies of individuals with acute or persistent concussion related symptoms.

The study will enroll a maximum of 50 subjects in each part, but may stop recruiting if each group has at least 20 participants who have completed the study.

5. Outcome Measures

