5.4 Safety Outcome Measures

Any laboratory, vital sign or ECG result meeting Common Terminology Criteria for Adverse Events (CTCAE), version 5.0, will be included in adverse event (AE) reports. Any unexpected findings on physical or neurological examinations will also be included in AE reports.

- Occurrence of any AEs commonly reported for OXE-103, CTCAE Grade 1 (mild) only.
- Occurrence of any unanticipated or unexpected (UU) treatment-emergent (TE) AE, UU serious AE (TE-SAE), UU AE leading to study drug discontinuation (TE-DAE), UU TE-AE related to study drug and UU TE-AE classified as Grade 2 or higher according to CTCAE, version 5.0. [Note that any AE commonly reported for OXE-103 that has CTCAE Grade 2 (moderate) or higher will be included among the UU TE-AEs.]
-
- Change from baseline in clinical laboratory parameters at each post-baseline assessment (Days 8, 15 and 21)
- Change from baseline in vital signs (including body weight) at each post-baseline assessment (Days 8, 15 and 44)
- Change from baseline in ECG intervals at each post-baseline assessment (Days 8, 15, 21)
- Change from baseline in Patient Health Questionnaire (PHQ)-9 total score at each post-baseline assessment (Days 8, 15 and 44)

6. Statistical Methods

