6.1 General Methods

This pilot study will describe changes observed in the two treatment groups, placebo versus OXE-103, separately for each part. Since the study is exploratory, analyses will focus on descriptive comparative statistics and not on a pre-specified statistically significant primary endpoint. Data will be used to enable power calculations and the definition of suitable clinical endpoints for further clinical development. Data from baseline and on Study Days 4, 8, 11, 15, 21, and 44 will be analyzed. Note that day definitions in this study will follow the Clinical Data Interchange Standards Consortium in that there is no Day 0;

assessments performed prior to randomization will be done on Days -7 and -3 (Part A only) and randomization is considered Day 1.

For all evaluations of changes from baseline, baseline is defined as the last reported value before the first dose of study drug. In most instances, this will be the value recorded on Day 1.

For the evaluation of safety, a treatment-emergent finding is any result that is newly reported after the first dose of study drug. This may include an existing condition which worsens in severity after the start of treatment.

Continuous variables such as total score or change from baseline will be summarized by the number of observations, mean, standard deviation, median, minimum and maximum value. Graphs of changes from baseline over time will present the means and 95% confidence intervals.

Binary or categorical variables will be summarized by the number of observations in each category along with the percent of observations.

To aid in interpretation of the importance of relationships, correlation coefficients (Pearson and Spearman) will be reported with p-values.

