6.9 Safety Analysis

AEs commonly reported for OXE-103 will be summarized for each treatment group, by study day of assessment and will include an 'At any time' category.

An overview of UU AEs will provide the number (%) of subjects in each treatment group with any TE-AE, TE-SAE, TE-DAE, TE-AE related to study drug,, and TE-AE classified as Grade 2 or higher according to CTCAE, version 5.0. Additionally, TE-AEs, related TE-AEs and Grade 2 or higher TE-AEs will be summarized for each treatment group by Medical Dictionary for Regulatory Activities (MedDRA) system-organ class (SOC) and preferred term (PT) as obtained from CTCAE, version 5.0. In these summaries, a subject may be counted only once for each PT and SOC. Details for any TE-SAEs or TE-DAEs will be provided in individual subject data listings.

Clinical laboratory test, vital sign (including body weight), ECG and PHQ-9 values and changes from baseline will be summarized with appropriate descriptive statistics for each treatment group and each visit.

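### The SAP lists suicide screening as a safety assessment but defines no subject-level outcome for it, so a newly positive screen may not be identifiable in the safety results

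*SAP*

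**What the plan says.** SAP section 2 (Study Design) names "vital signs including body weights, suicide screening and physical/neurological examination findings" alongside adverse events, laboratory samples and ECGs as the safety assessments. The SAP does not mention suicide screening again and ties no instrument to it.

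The only mood-related safety outcome is in SAP 5.4: "Change from baseline in Patient Health Questionnaire (PHQ)-9 total score at each post-baseline assessment (Days 8, 15 and 44". SAP 6.9 adds that "ECG and PHQ-9 values and changes from baseline will be summarized with appropriate descriptive statistics for each treatment group and each visit". SAP 6.1 says that continuous variables are "summarized by the number of observations, mean, standard deviation, median, minimum and maximum value".

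SAP 5.4 also sets out which results become adverse events: "Any laboratory, vital sign or ECG result meeting Common Terminology Criteria for Adverse Events (CTCAE), version 5.0, will be included in adverse event (AE) reports", and "Any unexpected findings on physical or neurological examinations will also be included in AE reports". PHQ-9 is in neither sentence. Individual listings in SAP 6.9 cover only treatment-emergent serious events and events leading to discontinuation of study drug.

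The protocol, under Depression Screening, gives the questionnaire an individual purpose: "The study team will administer the PHQ-9 questionnaire at specified timepoints to help identify any potential risk or need for intervention". The next paragraph, Safety Monitoring, says: "Subjects participating in Part A Arm 2 (non-treatment control) will not require safety monitoring". That arm's schedule nevertheless has PHQ-9 on Days 1, 8, 15 and 44, with no row for adverse effects. SAP 6.2 restricts the safety set to subjects who were dosed.

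**The concern.** A screen produces a result for one person: positive or not, new or not. A summary of total scores by group and visit answers a different question. If most subjects improve as they recover, the average can fall while one subject newly screens positive. The plan has no output that says how many such subjects there were, in which group, or at which visit.

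At stake is whether the safety report, and the adverse-event data sent to the independent medical monitor, can show a signal that the trial collects data to detect.

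**Working it through.** The plan states no figure to reproduce. The check sets the texts side by side and adds a small illustration.

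**1. Safety assessments in SAP 2 against SAP 5.4**

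| Assessment | Outcome in 5.4 | Rule making a result an adverse event |
|---|---|---|
| Adverse events | Occurrence | Not needed |
| Laboratory | Change, Days 8, 15, 21 | Yes |
| ECG | Change in intervals, Days 8, 15, 21 | Yes |
| Vital signs, weight | Change, Days 8, 15, 44 | Yes |
| Physical and neurological examination | None of its own | Yes |
| Suicide screening | None by that name; PHQ-9 total, Days 8, 15, 44 | None |

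Suicide screening is the only item with neither an outcome under its own name nor an adverse-event rule.

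**2. What the planned statistics can show**

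Take n = 20, the completer target per group. The score changes below are assumptions; the documents give none.

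- One subject's rise of d points moves the group mean by d/n. For d = 1, 3, 5 and 10 that is 0.05, 0.15, 0.25 and 0.50.
- One subject at +10 and 19 at -2: mean = (10 - 38)/20 = -1.4, median = -2.0, maximum = +10. The mean and median show improvement, but the maximum exposes the one subject.
- One at +10, one at +3 and 18 at -2: mean = (10 + 3 - 36)/20 = -1.15, median = -2.0, minimum = -2, maximum = +10. No planned statistic singles out the +3 subject.
- A total combines several answers. A worse answer offset by better ones leaves the total, and every statistic built on it, unchanged.

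The maximum is therefore a partial safeguard. It shows the largest rise, but not how many subjects rose, who they were, or whether any screen was newly positive.

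**3. How likely there is someone to count**

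P(at least one among 20) = 1 - (1 - p)^20, with p assumed:

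- p = 2%: 1 - 0.98^20 = 33%
- p = 5%: 1 - 0.95^20 = 64%
- p = 10%: 1 - 0.90^20 = 88%

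**4. Other routes into the safety results**

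For dosed subjects, the protocol's Adverse Events paragraph collects all events that subjects report, whatever the suspected cause. The Safety Monitoring section sends reported events to the medical monitor after 10 and after 30 subjects are enrolled. This route works only if someone records the screen result as an adverse event, and no text requires that for PHQ-9. By contrast, the protocol does require it for clinically significant ECG findings.

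**5. Part A Arm 2**

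PHQ-9 is collected at four time points, adverse events are not recorded, and no subject is dosed. By SAP 6.2 the arm is outside the safety set, which is used for all safety summaries. Its PHQ-9 data therefore enter none of them.

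**The case against.** The strongest reply is that the plan has more than one way to show a problem. A reader might infer that PHQ-9 is reported only as a mean change. That is not so: SAP 6.9 covers both values and changes, and SAP 6.1 adds the minimum and maximum, so a large rise in one subject can appear. A reader might also infer that a positive screen drops out of the safety results altogether. That too goes beyond the documents. In the dosed arms adverse effects are asked about at every contact, reported events are tabulated and sent to the monitor, and serious events and those leading to discontinuation are listed individually. The two routing sentences in SAP 5.4 do not say that nothing else may become an adverse event. These points stand; what is missing is an assured route, not every route.

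A second reply is that the documents never call PHQ-9 the suicide screen and describe neither its items nor a cut-off. That is correct, so the link remains an inference. If it is wrong, the gap is wider: a named safety assessment would have no instrument, schedule or analysis.

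Third, the two protocol paragraphs on Part A Arm 2 might be read as a flat contradiction. The list of changes for amendment 1.7 weakens that reading. It describes the safety activities not done in this arm as including adverse-event recording, laboratory tests and ECGs, and does not mention PHQ-9. The SAP is also dated November 2020, before the March 2021 protocol that describes the arm, so its silence there is a matter of version rather than a choice about PHQ-9. The protocol should still explain how the two statements fit together.

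Finally, this is an unpowered descriptive pilot with no mood or suicide objective, which limits how much rests on the point.

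**Conclusion.** The point holds in a limited form. The SAP names suicide screening but defines no subject-level outcome for it. PHQ-9 reaches the report only as total-score descriptive statistics and is absent from the adverse-event routing. A newly positive screen may therefore go uncounted, and unseen by the monitor, unless it is separately reported as an adverse event or happens to be the group's largest rise. In Part A Arm 2 the gap is complete as the SAP stands, because those data enter no safety summary.

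The size depends on a rate that the documents do not give: 33% to 88% for at least one such subject among 20, at assumed rates of 2% to 10%. The conclusion itself rests on the text, not on those figures. It does not follow that the trial can say nothing about mood, since PHQ-9 values and changes are still summarized for dosed subjects. This is a low-cost improvement to reporting, not a flaw in the efficacy analysis.

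**What to change.** The change is to reporting only.

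- Name the suicide-screening instrument in the SAP.
- Add to SAP 5.4 and 6.9 the number (%) and a listing, by group and visit, of subjects with a newly positive screen, as the sponsor defines it.
- Include that count and listing in the data sent to the medical monitor.
- Summarize PHQ-9 for every arm in which it is collected, including Part A Arm 2. This needs an analysis set that does not require a dose.
- State in the protocol how PHQ-9 screening in Part A Arm 2 fits with the statement that the arm requires no safety monitoring.

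The cost is one table, one listing and a sentence in the protocol. If PHQ-9 is the screen, the data are already collected. The SAP needs revision in any case, because it still describes Part A as randomized against placebo. No clinical threshold or management rule is proposed.

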5.1 Primary Efficacy Outcome Measures

- PCSS severity responder as defined by $\geq 20\%$ improvement over baseline at Day 15 in the severity score
- PCSS symptom responder as defined by $\geq 20\%$ improvement over baseline at Day 15 in the number of symptoms
- PCSS 4MBS responder as defined by $\geq 20\%$ improvement over baseline at Day 15 in the 4MBS severity score
- Change from baseline in PCSS severity score at each post-baseline assessment (Days 4, 8, 11, 15, 21 and 44)
- Change from baseline in PCSS number of symptoms at each post-baseline assessment (Days 4, 8, 11, 15, 21 and 44)
- Change from baseline in PCSS 4MBS severity score at each post-baseline assessment (Days 4, 8, 11, 15, 21 and 44)

5.2 Secondary Efficacy Outcome Measures

- Change from baseline in QOLIBRI total score at each post-baseline assessment (Days 4, 8, 11, 15, 21 and 44)
- Change from baseline in PGAS VAS at each post-baseline assessment (Days 4, 8, 11, 15, 21 and 44)
- Change from baseline in BrainCheck composite score at each post-baseline assessment (Days 4, 8, 11, 15, 21 and 44)

5.3 Exploratory Efficacy Outcome Measures

The exploratory study objectives may be assessed by examining responder rates on days other than the assessments done at the end of treatment (Day 15) or by examining relationships between primary and secondary outcomes. Therefore, there are no additional efficacy outcome measures to define.

5.4 Safety Outcome Measures

Any laboratory, vital sign or ECG result meeting Common Terminology Criteria for Adverse Events (CTCAE), version 5.0, will be included in adverse event (AE) reports. Any unexpected findings on physical or neurological examinations will also be included in AE reports.

- Occurrence of any AEs commonly reported for OXE-103, CTCAE Grade 1 (mild) only.
- Occurrence of any unanticipated or unexpected (UU) treatment-emergent (TE) AE, UU serious AE (TE-SAE), UU AE leading to study drug discontinuation (TE-DAE), UU TE-AE related to study drug and UU TE-AE classified as Grade 2 or higher according to CTCAE, version 5.0. [Note that any AE commonly reported for OXE-103 that has CTCAE Grade 2 (moderate) or higher will be included among the UU TE-AEs.]
-
- Change from baseline in clinical laboratory parameters at each post-baseline assessment (Days 8, 15 and 21)
- Change from baseline in vital signs (including body weight) at each post-baseline assessment (Days 8, 15 and 44)
- Change from baseline in ECG intervals at each post-baseline assessment (Days 8, 15, 21)
- Change from baseline in Patient Health Questionnaire (PHQ)-9 total score at each post-baseline assessment (Days 8, 15 and 44)

6. Statistical Methods

6.1 General Methods

This pilot study will describe changes observed in the two treatment groups, placebo versus OXE-103, separately for each part. Since the study is exploratory, analyses will focus on descriptive comparative statistics and not on a pre-specified statistically significant primary endpoint. Data will be used to enable power calculations and the definition of suitable clinical endpoints for further clinical development. Data from baseline and on Study Days 4, 8, 11, 15, 21, and 44 will be analyzed. Note that day definitions in this study will follow the Clinical Data Interchange Standards Consortium in that there is no Day 0;

assessments performed prior to randomization will be done on Days -7 and -3 (Part A only) and randomization is considered Day 1.

For all evaluations of changes from baseline, baseline is defined as the last reported value before the first dose of study drug. In most instances, this will be the value recorded on Day 1.

For the evaluation of safety, a treatment-emergent finding is any result that is newly reported after the first dose of study drug. This may include an existing condition which worsens in severity after the start of treatment.

Continuous variables such as total score or change from baseline will be summarized by the number of observations, mean, standard deviation, median, minimum and maximum value. Graphs of changes from baseline over time will present the means and 95% confidence intervals.

Binary or categorical variables will be summarized by the number of observations in each category along with the percent of observations.

To aid in interpretation of the importance of relationships, correlation coefficients (Pearson and Spearman) will be reported with p-values.

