- 1. Describe the change in symptom burden in sub-acute (Part A) and acute (Part B) concussion for the two groups.** This aim defines our primary objective. In Part A we will enroll a maximum of 30 subjects in the open-label treatment Arm (OXE-103) but will stop recruiting when that arm has 20 participants who have completed study requirements. All Part A participants must be diagnosed with a concussion and experience persistent concussion symptoms \leq 28 days post injury. The Part A non-treatment concurrent control Arm will enroll a minimum 20 participants who complete the study requirements, but may continue to recruit more than 20 participants while the Part A open-label treatment Arm is still recruiting. In Part B we will enroll a maximum of 50 subjects but will stop recruiting after each arm (OXE-103 Arm and placebo Arm) has 20 participants who have completed the study requirements. In Part A subjects will receive OXE-103 open-label and in Part B we will randomize 1:1 to placebo versus OXE-103. The Post-Concussion Symptom Score questionnaire (PCSS) will be used as an overall measure of symptom burden. The number of symptoms and severity at each time point are also measures of interest. In addition, subjects will be asked to identify and rank the 4 most bothersome symptoms. We hypothesize that changes in these most bothersome symptoms may have a higher correlation to improvement in quality of life. A visual comparison of change in the two groups will be made. We will consider a change of 20% to be clinically meaningful. Our primary aim will describe the change in symptoms between day 1 and day 15.
- 2. Describe the change in quality of life between the two groups.** This aim defines one of our secondary objectives. To assess this, we will administer the Quality of Life after Brain Injury scale (QOLIBRI) and a Patient Global Assessment of Status (PGAS). A change of 20% will be considered clinically meaningful. Our primary objective with this aim will assess the change between days 1 and 15.
- 3. Describe the correlation between the change in symptom burden and quality of life.** This is an exploratory aim. We hypothesize that improvement in symptom burden will correlate with improvement in quality of life measures. This may be more evident in the correlation between the change in the 4 most bother symptoms and quality of life measures. This aim will describe this correlation between days 1 and 15.

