Subjects will complete the PCSS at the following timepoints[17]: upon signing consent (score must ≥ 20) (Day 1), as well as days 4, 8, 11, 15, 21 and 44. Subjects will be instructed to record their symptoms at the same time of day for each assessment timepoint. There can be a two-hour window either way. (e.g. 12PM +/- 2 hrs.). The PCSS is a self-reported assessment of 22 symptoms using a Likert-type scale ranging from 0-6, with 0 indicating no difficulty with the outlined symptom and ratings of 1-6 representing mild-to-severe difficulty with the symptom. The reliability and validity of the PCSS are well documented [18-20]. We will also ask subjects to rank their 4 most burdensome symptoms (4MBS) at Day 1 and we will analyze these separately. As stated in the Specific Aims the purpose of this study is to collect data that would further refine clinical endpoints that could be used for larger Phase 2 studies and possibly lead to the establishment of pivotal endpoints for Phase 3 registration trials. The 22 symptom PCSS assessment is designed to cover the full spectrum of concussion related symptoms across cognitive, emotional and somatic domains. In that regard the PCSS is particularly useful for diagnosis and monitoring recovery of patients post injury. However, due to the number of symptoms across cognitive, emotive and somatic domains, resolution of several mild symptoms may result in a change in the overall symptom score with relatively minor clinical impact on the patient's well-being. Pre-IND feedback already obtained from the FDA has noted that an effective therapy for concussion must impact the way a patient feels or functions. By including a specific analysis of the patient perceived 4MBS we are likely to be able to correlate symptom scores with improvement in the quality of life tools also being used in the study. The completion of the PCSS will take an estimated 5 minutes.

Quality of Life (AIM 2): A secondary goal is to examine change in quality of life with treatment of acute and sub-acute concussion. We hypothesize that OXE-103 will reduce symptoms when comparing days 1 and 15 and therefore improve quality of life as assessed by 1) Quality of Life after Brain Injury scale (QOLIBRI) and 2) a PGAS.

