6.8 Efficacy Analysis

As described previously, binary variables (responders) and continuous variables (values and changes from baseline) will be summarized with appropriate descriptive statistics for each treatment group and each visit (as needed). Changes from baseline over time will also be presented graphically with means (95% confidence intervals) with both treatment groups presented on the same figure.

To evaluate the appropriateness of the current responder definitions, a Receiver Operating Characteristic (ROC) analysis will be performed for each response outcome measure. The current definitions indicate that a ≥20% improvement over baseline is required for a subject to be considered a responder. In the ROC analysis, the percent improvement will be varied from 5% to 95% to determine which percentage is best for distinguishing OXE-103 treated subjects from placebo subjects. If data suggest an early treatment response, the ROC analysis may be performed for a time point earlier than Day 15.

FDA pre-IND guidance from the FDA on the clinical development of OXE-103 advised that “***The outcome measure should be constructed in a way that ensures that a score change is indicative of a meaningful improvement in how a patient feels or functions that comes from a treatment effect specific to mild TBI.***” Pearson and Spearman correlation coefficients (and p-values) will be calculated to examine

relationships between the PCSS changes and changes in the quality of life measures (QOLIBRI total score and PGAS VAS).

Relationships between PCSS changes and changes in cognition and balance (BrainCheck composite measure) will also be examined using correlation coefficients.

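### The protocol expects 4MBS change to track quality of life more closely than total PCSS change, but the SAP plans only coefficients and p-values, with no interval for any correlation or for the difference between them

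*SAP*

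**What the plan says.** The comparative idea appears three times in the Protocol. Under Specific Aims, Aim 1 states: "We hypothesize that changes in these most bothersome symptoms may have a higher correlation to improvement in quality of life". Aim 3, labelled exploratory, repeats it: "This may be more evident in the correlation between the change in the 4 most bother symptoms and quality of life measures". Outcomes & Study Tools (symptom reduction) gives the reason. Several mild symptoms can resolve and move the 22-item total with little clinical effect, whereas "By including a specific analysis of the patient perceived 4MBS we are likely to be able to correlate symptom scores with improvement" on the quality-of-life tools.

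SAP section 3 restates the objective without the comparison: "Describe the correlation between the change in symptom burden and quality of life during the treatment period for each group in each part". For the analysis, SAP 6.1 says: "To aid in interpretation of the importance of relationships, correlation coefficients (Pearson and Spearman) will be reported with p-values". SAP 6.8 adds: "Pearson and Spearman correlation coefficients (and p-values) will be calculated to examine" how PCSS changes relate to changes in QOLIBRI total and PGAS VAS. Intervals are planned for something else: "Graphs of changes from baseline over time will present the means and 95% confidence intervals". SAP 6.13 rules out modelling. On size, SAP section 4 says the study "may stop recruiting if each group has at least 20 participants who have completed the study", and SAP 6.2 uses the per-protocol set for efficacy summaries.

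**The concern.** Whether 4MBS change tracks quality of life better than total PCSS change is a question about the difference between two correlations that share the same subjects and the same quality-of-life variable. The usual p-value for a correlation asks whether that one coefficient is zero. It does not measure importance or say which of two coefficients is larger. In a recovering condition symptoms and quality of life would be expected to move together, so zero is not an informative reference.

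SAP 6.1 lists the definition of suitable clinical endpoints among the uses of these data, so the comparison feeds the choice between 4MBS and the total score in later trials. If p-values are the only guide to uncertainty, a reader may take a small p for one measure and a larger p for the other as evidence that the first tracks quality of life better.

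**Working it through.** The documents give no alpha, power or target correlation for this analysis, so there is no planned figure to reproduce.

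**Inputs.** n=20 per arm is the completer target (SAP section 4); the per-protocol n may differ. Assumed, because the documents do not say: two-sided 0.05; a true correlation with quality of life of 0.4 to 0.7; a correlation between 4MBS change and total PCSS change of 0.7 to 0.9. The last is plausible because the four items are among the 22.

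**1. What p<0.05 means at this size.** Critical r = t/√(n−2+t²). For n=20, t=2.101 on 18 df, so r = 2.101/√(18+4.414) = 0.444. The same formula gives 0.514 at n=15 and 0.396 at n=25.

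**2. Uncertainty in one coefficient.** The Fisher interval is tanh(atanh r ± 1.96/√(n−3)), with 1.96/√17 = 0.475.
- r=0.45: 0.485 ± 0.475 gives 0.01 to 0.74, p=0.047.
- r=0.40: 0.424 ± 0.475 gives −0.05 to 0.72, p=0.081.

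Two nearly identical correlations fall on opposite sides of 0.05.

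**3. Comparing two p-values when the true correlations are equal.** Simulation of trivariate normal data, n=20, 200,000 samples per cell. Each cell shows the percentage of samples with exactly one correlation at p<0.05, then the percentage with 4MBS alone.

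| True r (both) | 4MBS–total 0.7 | 0.8 | 0.9 |
|---|---|---|---|
| 0.40 | 27 / 14 | 22 / 11 | 16 / 8 |
| 0.45 | 28 / 14 | 23 / 11 | 16 / 8 |
| 0.50 | 26 / 13 | 22 / 11 | 15 / 8 |
| 0.60 | 18 / 9 | 15 / 7 | 10 / 5 |
| 0.70 | 7 / 3 | 5 / 3 | 4 / 2 |

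**4. What an interval for the difference would show.** Zou's method for dependent correlations, for observed r₁=0.6 (4MBS), r₂=0.4 (total), r₁₂=0.8, n=20:
- Separate intervals: 0.214 to 0.824 and −0.052 to 0.716.
- Correlation between the two estimates: c = [(r₁₂−½r₁r₂)(1−r₁²−r₂²−r₁₂²)+r₁₂³]/[(1−r₁²)(1−r₂²)] = [0.68×(−0.16)+0.512]/(0.64×0.84) = 0.75.
- Lower limit: 0.2 − √(0.386²+0.316²−2×0.75×0.386×0.316) = −0.06.
- Upper limit: 0.2 + √(0.224²+0.452²−2×0.75×0.224×0.452) = 0.52.

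With r₁₂=0.7 the interval is −0.11 to 0.56, and with 0.9 it is 0.01 to 0.48. At n=40 (two arms pooled) with r₁₂=0.8 it is 0.03 to 0.41.

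**5. Number of p-values.** PCSS with quality of life at Day 15: 3 PCSS measures × 2 quality-of-life measures × 2 coefficients × 4 arms = 48. The 4MBS-versus-total contrast uses 2×2×2×4 = 32 of them.

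**6. Choice of interval.** With both true correlations 0.5 and r₁₂=0.8, coverage of a nominal 95% interval for the Pearson difference at n=20 was about 95% for Zou's method (40,000 samples). It was about 92% for a percentile paired bootstrap and 89% for BCa (3,000 samples each, 1,000 resamples). For the Spearman difference (1,500 samples) the percentile bootstrap covered 97% and BCa 93%.

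**The case against.** The aim is exploratory, is worded as describing a correlation, and says only that 4MBS may do better. The SAP makes no claim of power, sets no alpha, and takes precedence over the Protocol on analyses. Its own objective asks for a description by group and part. It reports the coefficients, so the two can be compared by eye. All of this stands, and it limits the point to a reporting improvement. It does not remove it: the Protocol, dated after the SAP, still carries the comparative hypothesis, and a description of a difference at n=20 is incomplete without its uncertainty.

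Three stronger readings should be avoided.
- A reader might infer that the SAP does nothing but test each correlation against zero. It does not: point estimates are reported.
- A reader might infer that the endpoint will be chosen by comparing p-values. No such rule exists; the SAP's wording about importance only invites that use.
- A reader might take the 4% to 28% as the rate of falsely favouring 4MBS. That range counts both directions; the one-directional rate is about half, and it falls to 2% to 3% if the true correlations are near 0.7.

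Nor is multiplicity the main issue. Adding BrainCheck would raise the count from 48 to 72, but it is not a quality-of-life measure, and no error rate is claimed.

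**Conclusion.** The point holds as a modest one. The Protocol poses a comparison between two dependent correlations; the SAP supplies point estimates and p-values, with no interval for either coefficient or for their difference. At 20 per arm the p-value amounts to a threshold of about 0.44 on |r|. Under the assumed equal correlations, contrasting two p-values would wrongly single out one measure in about 4% to 28% of samples, and 4MBS in about 2% to 14%. These rates rest on normality, two-sided 0.05, n=20 and correlations that the documents do not give. The critical value and the interval for a single r need only n and the usual normal-theory formulas.

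**What to change.** In SAP 6.1 and 6.8, replace the p-values with 95% confidence intervals for each coefficient. For Aim 3, add the difference r(4MBS change, QoL change) minus r(total PCSS change, QoL change), separately for QOLIBRI and PGAS. Sign every change so that improvement is positive, since the scales run in opposite directions.

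Use an interval built for dependent correlations. Zou's method suits Pearson. A paired bootstrap is the alternative and is needed for Spearman; name the type in advance, because for Pearson both percentile and BCa versions under-covered at n=20 in the setting checked.

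Lead with estimates by arm within each Part, as the SAP objective states. A pooled estimate with arm means subtracted can support them, mainly in randomised Part B. It assumes a common correlation in both arms, which should be stated and is doubtful in Part A, where subjects choose between open-label treatment and no treatment.

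Label the result as estimation for planning. The interval will be wide and will rarely separate the two measures. The cost is SAP wording and a short program, with no new data. The SAP needs revision anyway, because section 2 still describes Part A as randomised and placebo-controlled.
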